8 ASSESSMENT OF SAFETY

Patients will be monitored for signs and symptoms of adverse events (AEs) throughout the study by a qualified oncologist/hematologist, with experience in clinical research. All AEs will be reported in the case report form (CRF), including seriousness, NCI-CTCAE grade severity, causal relationship to the study medication, and action taken. If AEs occur, the first concern will be the safety of the study participant.

8.1 ADVERSE EVENT DEFINITIONS (21 CFR§312.32)

• Adverse event (AE) means any untoward medical occurrence associated with use of a drug in humans, whether or not considered drug related. (The term treatment emergent adverse event [TEAE] covers any unfavorable and unintended sign, symptom, syndrome, or illness that develops or worsens during the period of observation in the clinical study). Surgical or other procedures themselves are not TEAEs. The condition for which the surgery/other procedure is required is a TEAE, if it occurs or is detected during the study period. Planned surgical or other procedures planned/permitted by the study protocol and the condition(s) leading to these measures are not TEAEs, if the condition(s) was (were) known before the start of study treatment. In the latter case the condition should be reported as medical history.

- **Suspected adverse reaction (SAR)** means any AE for which there is a reasonable possibility that the drug caused the AE. A "reasonable possibility" means there is evidence to suggest a causal relationship between the drug and the adverse event, such as:
 - A single occurrence of an event that is uncommon and known to be strongly associated with drug exposure (e.g., angioedema, hepatic injury, Stevens-Johnson Syndrome);
 - One or more occurrences of an event that is not commonly associated with drug exposure, but is otherwise uncommon in the population exposed to the drug (e.g., tendon rupture);
 - An aggregate analysis of specific events observed in a clinical trial (such as known consequences of the underlying disease or condition under investigation or other events that commonly occur in the study population independent of drug therapy) that indicates those

events occur more frequently in the drug treatment group than in a concurrent or historical control group.

SAR implies a lesser degree of certainty about causality than adverse reaction, which means any AE caused by a drug.

- Adverse reaction (AR) means an AE caused by the drug.
- Serious adverse event (SAE) or serious suspected adverse reaction (SSAR) is an event that, in the view of either the investigator or sponsor, results in any of the following outcomes:
 - Death occurring within 4 weeks after the last administration study drug, irrespective of cause, or within any interval if related to the study drug
 [Although death may occur as a result of the basic disease process, all deaths occurring

within 30 days of the last administration of study drug must be managed as SAEs and reported as such. Additionally, all deaths that may be considered as related to the study drug, regardless of the interval, must be treated as SAEs and reported as such.];

- A life-threatening adverse event;
- Inpatient hospitalization or prolongation of existing hospitalization;
- A persistent or significant incapacity or substantial disruption of the ability to conduct normal life functions; or
- A congenital anomaly/birth defect.

In addition, medical and scientific judgment should be exercised in deciding whether expedited reporting is appropriate in situations where none of the outcomes listed above occurred. Important medical events that may not be immediately life-threatening or result in death or hospitalization but may jeopardize the patient or may require intervention to prevent one of the other outcomes listed in the definition above should also usually be considered serious. Examples of such events include overdose even not complicated, or AE requiring intensive treatment without hospitalization. A diagnosis of a new cancer type during the course of a treatment should be considered as medically important. In addition, any pregnancy diagnosed in a female subject on treatment with the investigational product or in the partner of a male subject on treatment with the investigational product or to the sponsor immediately. The List of Critical Terms (1998 adaptation of WHO Adverse Reaction Terminology Critical Terms List, provided in the "Instructions for completing the 'Serious Adverse Event/Expedited Report from a Clinical Trial' form") should be used as guidance for adverse events that may be considered serious because they are medically important.

Finally, for the purpose of this phase I study, any suspected DLT will be considered as medically important and reported as SAE, even if it does not meet other criteria for seriousness. In the latter case, the reason for seriousness will be "other important medical event". The specific SAE report form for this study includes a box "DLT: Yes/No"

• Life-threatening adverse event or life-threatening suspected adverse reaction is an AE that, in the view of either the investigator or sponsor, places the patient or subject at immediate risk of death. It does not include an AE or suspected adverse reaction that, had it occurred in a more severe form, might have caused death.

The information in this document is the property of OncoEthix and is confidential. Neither the document nor the information contained therein may be reproduced or disclosed outside OncoEthix without their written consent

• Unexpected adverse event or unexpected suspected adverse reaction is an AE or suspected adverse reaction that is not listed in the investigator brochure or is not listed at the specificity or severity that has been observed. For example, under this definition, hepatic necrosis would be unexpected (by virtue of greater severity) if the investigator brochure referred only to elevated hepatic enzymes or hepatitis. Similarly, cerebral thromboembolism and cerebral vasculitis would be unexpected (by virtue of greater specificity) if the investigator brochure listed only cerebral vascular accidents. "Unexpected", as used in this definition, also refers to AEs or suspected adverse reactions that are mentioned in the investigator brochure as occurring with a class of drugs or as anticipated from the pharmacological properties of the drug, but are not specifically mentioned as occurring with the particular drug under investigation.

8.2 DOCUMENTATION OF ADVERSE EVENTS

Each and every TEAE occurring during the course of the study, whether or not considered related to the study drug or to underlying disease, must be individually recorded in the CRF, including the nature of the event, date and time of onset (where appropriate), duration of effect, action taken, seriousness, severity, and relationship to study medication. Any consequent change to the dosage schedule or any corrective therapy should be recorded.

Every attempt should be made to describe the TEAE in terms of a diagnosis. If a clear diagnosis has been made, individual signs and symptoms will not be recorded. If a clear diagnosis cannot be established, each sign and symptom must be recorded individually.

All subjects who experience a TEAE, regardless of the relationship to study treatment, must be monitored to determine the outcome. The clinical course of the adverse event will be followed up even after the end of the period of observation, until a satisfactory explanation is found or the investigator considers it medically justifiable to terminate follow-up. Should the adverse event result in death, post-mortem examination should be considered as far as possible.

After last study treatment administration, patient will be observed during at least 30 days to document any late side effect and until resolution in case of AE thought to be related to study treatment, and every month and a half for the first three months, then every three months until death.

AEs already recorded and designated as "continuing" should be reviewed at each subsequent assessment. If resolved, details are to be recorded in the CRF. If an AE changes for the worse, in frequency of attacks/symptoms or in severity, a new record of the event must be started (i.e., distinct AE reports are required for differing frequencies and/or severity of the same event to enable comprehensive safety reports and later analysis).

Diagnostic and therapeutic non-invasive and invasive procedures, such as surgery, must be reported under "concomitant procedures" in the CRF and not as an AE. The medical condition for which the procedure was performed must be reported.

The information in this document is the property of OncoEthix and is confidential. Neither the document nor the information contained therein may be reproduced or disclosed outside OncoEthix without their written consent

A clinical laboratory abnormality should be reported as an AE only if the abnormality is "clinically significant", i.e. the abnormality is serious, OR requires active management (e.g., specific treatment, change or delay of dose, discontinuation of study drug, more frequent follow-ups, and diagnostic investigation) OR is considered as a toxicity of the study treatment.

8.2.1 AE Grade

All AEs, whether or not they are considered related to the study drug, must be graded using the NCI Common Toxicity Criteria for Adverse Events (CTCAE) Version 4.02 [http://evs.nci.nih.gov/ftp1/CTCAE/CTCAE_4.02_2009-09-15_QuickReference_8.5x11.pdf]. The worst grade for that particular event is to be documented.

AE grades usually reflect their severity, with grade 1 meaning "mild", grade 2 meaning "moderate", grade 3 meaning "severe", grade 4 meaning "life-threatening" and grade 5 meaning "fatal".

8.2.2 AE Severity

The term "severity" is used to describe the **intensity** of an adverse event; the event itself, however, may be of relatively minor clinical significance (e.g., 'severe' headache). This is **not** the same as "serious". Seriousness of AEs is based on the outcome/action of an AE and usually is associated with events that pose a threat to a patient's life or functioning.

Intensity of the adverse event will be evaluated using the following criteria:

- Mild: The patient is aware of the sign or symptom, but finds it easily tolerated. The event is of little concern to the patient and of little clinical significance. The event is not expected to have any effects on the patient's overall health or well-being.
- **Moderate**: The patient has discomfort enough to cause interference with or change in usual activities. The event is of some concern to the patient's health or well-being and may require medical intervention and/or close follow-up.
- Severe: The adverse event interferes considerably with the patient's usual activities. The event is of definite concern to the patient and/or poses substantial risk to the patient's health or wellbeing. The event is likely to require medical intervention and/or close follow-up and may be incapacitating or life-threatening. Hospitalization and treatment may be required.

8.2.3 Adverse event relationship to study treatment or procedure

All TEAEs occurring during treatment with an investigational agent may be related to the investigational agent. All TEAEs, regardless of the supposed relationship to study treatment, must therefore be collected. However, the investigator often has arguments to think that a TEAE is or is not related to the study treatment. Albeit subjective, and susceptible to be challenged, the assessment of relationship to study treatment is an important role of the investigator. Thus, the investigators should decide, based on their knowledge and medical expertise, whether, in their opinion, an AE is "reasonably related" or "unlikely related" to the study treatment (or to study specific procedures).

8.3 EVENTS OF CLINICAL INTEREST

Selected non-serious and serious adverse events are also known as Events of Clinical Interest (ECI) and must be reported to the Sponsor.

For the time period beginning when the consent form is signed until patient registration, any ECI, or follow up to an ECI, that occurs to any patient must be reported within 24 hours to the Sponsor if it causes the subject to be excluded from the trial, or is the result of a protocol-specified intervention, including but not limited to washout or discontinuation of usual therapy, diet, or a procedure.

For the time period beginning at patient registration through 30 days following cessation of treatment, any ECI, or follow up to an ECI, whether or not related to the Sponsor's product, must be reported within 24 hours to the Sponsor, either by electronic media or paper. Electronic reporting procedures can be found in the data entry guidelines.

 An elevated AST or ALT lab value that is ≥3X ULN and an elevated total bilirubin lab value that is ≥2X ULN and, at the same time, an alkaline phosphatase lab value that is < 2X ULN, as determined by protocol-specified laboratory testing or unscheduled laboratory testing.*

*Note: These criteria are based upon available regulatory guidance documents. The purpose of the criteria is to specify a threshold of abnormal hepatic tests that may require an additional evaluation for an underlying etiology. The trial site guidance for assessment and follow up of these criteria can be found in Appendix 5 and the Investigator Brochure section on discussion and guidance for investigator.

- 2. An elevated total bilirubin lab value that is > 2X ULN.
- 3. Any of the following liver test abnormalities are observed (see also Appendix 3):
 - ALT or AST > 8X ULN
 - ALT or AST > 5X ULN for more than 2 weeks
 - ALT or AST > 3X ULN AND (total bilirubin > 2X ULN OR INR > 1.5)
 - ALT or AST > 3X ULN with the appearance of fatigue, nausea, vomiting, right upper quadrant pain or tenderness, fever, rash and/or eosinophilia (> 5%), unless the investigator assesses the rash or fatigue to be related to OTX015 and not related to liver impairment with sponsor's agreement.

**All patients with these liver test abnormalities should be followed weekly until all abnormalities return to normal or to the baseline state. DILI may develop or progress even after the causative drug has been stopped. Results should be recorded on the case report form and in the database. See Appendix 16.12 for guidelines on the handling of events of ALT or AST >3 x ULN AND total bilirubin >2 x ULN or INR>1.5 (potential Hy's law cases).

8.4 IMMEDIATE REPORTING BY INVESTIGATOR TO SPONSOR

SAEs and other events that fulfill a reason for expedited reporting to Pharmacovigilance (overdose and pregnancy and DLT for the present study) must be documented on a "Serious Adverse Event Report Form" (SAERF) at the time the SAE is detected. This form must be completed and sent within 24 hours, or at the latest on the following working day to the sponsor's Pharmacovigilance representative:

The information in this document is the property of OncoEthix and is confidential. Neither the document nor the information contained therein may be reproduced or disclosed outside OncoEthix without their written consent

The SAERF and the guidelines for filling it in are provided in the investigator's study file.

The sponsor will ensure that all legal reporting requirements are met.

The initial report must be as complete as possible, including details of the current illness and (serious) adverse event, and an assessment of the causal relationship between the event and the investigational product(s).

Information not available at the time of the initial report (e.g., an end date for the AE or laboratory values received after the report) must be documented on a follow-up SAERF.

8.5 PERIOD OF OBSERVATION

For the purposes of this study, the period of observation for collection of AEs extends from the start of treatment with investigational product until the end of study treatment (i.e. 30 days after the last study drug administration), except for adverse events related to study drug, which must be reported during follow-up period until resolution or change of causality from related to non-related or initiation of further antitumor therapy.

If the investigator detects a SAE in a study subject after the end of the period of observation, and considers the event possibly related to prior study treatment, he or she should contact the sponsor to determine how the adverse event should be documented and reported.

9 STUDY TREATMENT DISCONTINUATION

Study treatment will be definitely discontinued for the following reasons:

- Patient's request (consent withdrawal) at any time without need for any justification
- If, in the investigator's opinion, the benefit/risk ratio is no longer favorable and continuation in the study could be detrimental to the subject. This includes:
- 1. Progressive disease
- 2. Intolerable toxicity
- 3. Treatment interruption > 2 weeks due to TEAEs (except in cases of suspicion of hematologic DLT in acute leukemia, where treatment interruption for 3 weeks is allowed to confirm DLT) related to the study medication, unless the investigator thinks resuming study treatment is the best patient's interest
- 4. Recurrence of the same toxicity, with the same severity after one dose reduction, unless the investigator thinks pursuing study treatment at lower dose is the best patient's interest, with sponsor's agreement
- 5. Lack of patient compliance
- 6. Major protocol deviation
- 7. Any of the following liver test abnormalities (see Appendix 5)
 - ALT or $AST > 8 \times ULN$
 - ALT or AST $> 5 \times ULN$ for > 2 weeks
 - ALT or AST $> 3 \times ULN$ and (total bilirubin $> 2 \times ULN$ OR INR > 1.5)
 - ALT or AST > 3 x ULN with the appearance of fatigue, nausea, vomiting, right upper quadrant pain or tenderness, fever, rash and/or eosinophilia (>5%), unless the investigator assesses the rash or fatigue to be related to OTX015 and not related to liver impairment with sponsor's agreement.
- Upon specific request of the sponsor

In all cases, the reason for and date of study treatment discontinuation must be recorded in the CRF at the "End of Study Treatment" page and source documented in the patient's medical records. As far as possible, there should be only one reason for study treatment discontinuation. If there are several reasons (e.g.; concomitant progressive disease and toxicity), efforts will be made to select the most important one (i.e. the reason that would have been sufficient, should it occur alone). The subject must be followed up to establish whether the reason was a TEAE, and, if so, this must be reported as such (see Section 8.2).

As far as possible, all examinations scheduled for the final study day must be performed on all subjects who receive the investigational product but do not complete the study according to protocol.

The investigator must make every effort to contact subjects lost to follow-up. Especially, when a patient is treated in another, non-study, center, the investigator is responsible for collecting follow-up data from this center.

Subjects early withdrawn from study (i.e. those receiving less than 18 days of treatment for the continuous, 21-day schedule or less than 12 days of treatment for the intermittent, 14 days ON/ 7 days OFF schedule), or those having received < 85% of the intended cumulative dose during the first 21 days and who do not experience a DLT; (i.e. patients not evaluable for DLT, the primary study endpoint) will be replaced.

After study withdrawal, patients' care will be managed in their best interest, by the investigator and/or the referring physician

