• Dosing interruption for > 2 weeks due to toxicity, recurrence of the same toxicity with the same severity despite one dose reduction, or specific liver toxicities* will lead to definitive study treatment discontinuation, unless the investigator thinks the patient's best interest is to pursue study treatment, with sponsor's agreement.

* Any of the following liver test abnormalities** (see Appendix 16.12)

- ALT or $AST > 8 \times ULN$
- ALT or $AST > 5 \times ULN$ for > 2 weeks
- ALT or AST > 3 x ULN AND (total bilirubin > 2 x ULN OR INR > 1.5)

ALT or AST > 3 x ULN with the appearance of fatigue, nausea, vomiting, right upper quadrant pain or tenderness, fever, rash and/or eosinophilia (> 5%), unless the investigator assesses the rash or fatigue to be related to OTX015 and not related to liver impairment with sponsor's agreement.

**Note: All patients with these liver test abnormalities should be monitored weekly until all abnormalities return to normal or to the baseline state. For patients with isolated total bilirubin increases >2 x ULN or 2 x baseline (if elevated at baseline), except if associated with direct bilirubin \leq ULN, monitoring should be every 2 weeks until bilirubin returns to normal or to the baseline state. Drug induced liver injury (DILI) may develop or progress even after the causative drug has been stopped. Results should be recorded on the CRF and in the database. See guidelines on the handling of these events (potential Hy's law cases).

Premedication

No premedication is planned at the first cycle, in the first 3 patients. Decision of further systematic premedication should be taken by the SMC.

Dose escalation scheme:

• The starting dose will be 10 mg/day (once a day, flat dose, without adaptation for body weight or surface area),

• DLTs will be collected during the first cycle (21 days after the first OTX015/MK-8628 administration) The dose escalation scheme will be as follows for each subset (AL and other hematological malignancies). The magnitude of dose escalation between two consecutive dose levels will depend upon the occurrence or not of DLT at the current DL.

Dose Level					
1 (starting dose) (mg)	10				
2	20				
3	30	40			
4	40	60	80		
5	50	80	120		
Dose escalation schedule:					
Doubling the dose in the absence of DLT (grey boxes).					
Fibonacci-lik	te model once at least one D	DLT occurs (white boxes)			

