3.1.1 Dose escalation part

- Two dose escalation subsets will be assessed independently in parallel: patients with acute leukemia and patients with other hematological malignancies.
- Patients will be enrolled by successive cohorts of 3 patients in each dose escalation subset.
- Three patients will be initially treated at the starting dose level (DL) in each subset. If no dose limiting toxicity (DLT) is observed among these 3 patients during the first cycle of treatment (i.e. the first 21 days following study treatment initiation, regardless of the treatment schedule), the next 3 patients will be treated at the DL immediately above, according to the dose escalation schedule defined in section 5.2.4.1. In the absence of DLT observed at the completed DL, the dose will be doubled.

- At each DL in each subset, the second patient enrolled will not start the study treatment before the first treated patient of the cohort will have completed at least 2 weeks of treatment (i.e. 14 consecutive daily administrations). The first patient enrolled in a higher DL cohort will not start the study treatment before the last treated patient in the DL immediately below will have completed at least one cycle of study treatment (i.e. 21 days following study treatment initiation, regardless of the treatment schedule)..
- If one out of 3 patients of a cohort experiences a DLT during the first cycle (i.e. 21 days following study treatment initiation, regardless of the treatment schedule), 3 additional patients will be entered at this DL. If no more than 1/6 treated and evaluable patient experience a DLT, the dose escalation will proceed to the DL immediately above. As soon as a DLT is observed, the magnitude of dose escalation will follow a Fibonacci-like model. (see section 5.2.4.1).
- If more than one patient out of 6 (or more than one out of 3) patients experiences a DLT, the DL will be considered exceeding the maximum tolerated dose (MTD) for this subset.
- Patients not evaluable for DLT are those having received less than 85% of the intended cumulative dose during the first 21 days (i.e. those receiving less than 18 days of treatment for the continuous, 21-day schedule or less than 12 days of treatment for the intermittent, 14 days ON/ 7 days OFF schedule) and who have not experienced a DLT, will be replaced.

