11.2 ANALYSIS POPULATIONS

- Intent-to-treat population: all enrolled patients
- **Per protocol population**.: all enrolled patients with no violation of inclusion/exclusion criteria
- Evaluable for safety population: all patients having received at least one dose of OTX015
- Evaluable for DLT population: all treated patients having received at least 85% of the intended dose during the first cycle (i.e. ≥ 12 days at full dose for AL and ≥ 18 days at full dose for other hematological malignancies)* of OTX015/MK-8628 treatment, as well as patients not fulfilling these conditions, but having experienced a DLT.

*e.g. for DL1 (10 mg/day), patients with AL having received \geq 120 mg over the first 21 days (10 mg x 12), or patients with other hematological malignancies having received \geq 180 mg over the first 21 days (10 mg x 18).

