# 8. POPULATIONS

Enrolled Population: all patients who signed an Informed Consent Form.

Treated/Safety Population: all included patients receiving at least one dose of the investigational drug.

**Evaluable for Efficacy Population:** All treated patients with at least one available tumor assessment (BM aspiration for AL patients or imaging for OHM patients) by the end of cycle 2 or later, OR with earlier evidence (i.e. cycle 1) of response or progression.

**Evaluable for DLT Population:** all treated patients receiving at least 85% of the intended OTX015/MK-8628 dose during the first cycle (i.e.  $\geq$  12 days at full dose for AL and  $\geq$  18 days at full dose for other hematologic malignancies)\*, as well as patients not fulfilling these conditions, but who experienced DLT.

\*e.g. for DL1 (10 mg/day), AL patients receiving  $\geq$  120 mg over the first 21 days (10 mg x 12), or other hematologic malignancy patients receiving  $\geq$  180 mg over the first 21 days (10 mg x 18).

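### DLT evaluability rests on cycle 1 dose taken (or a DLT), with no requirement of assessment to day 21, so on 14/21 a patient lost after dose 12 counts as DLT-free

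*Protocol*

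**What the plan says.** The DLT window is the same on every schedule. The Protocol synopsis states: "DLTs will be collected during the first cycle (21 days after the first OTX015/MK-8628 administration"; Protocol 3.1.1 and 3.2 repeat the 21 days regardless of schedule.

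Evaluability and replacement are set by dose:

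- Protocol 3.1.1: "Patients not evaluable for DLT are those having received less than 85% of the intended cumulative dose during the first 21 days".
- Protocol 9 gives the day counts, "Subjects early withdrawn from study (i.e. those receiving less than 18 days of treatment for the continuous, 21-day schedule or less than 12 days" on the intermittent schedule, and adds "those having received < 85% of the intended cumulative dose during the first 21 days and who do not experience a DLT". Such patients are replaced.
- Protocol 11.2 defines the DLT population as "all treated patients having received at least 85% of the intended dose during the first cycle", plus anyone who had a DLT.
- SAP 8 carries this over: "all treated patients receiving at least 85% of the intended OTX015/MK-8628 dose during the first cycle", again plus anyone with a DLT. The SAP synopsis repeats the replacement rule.

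None of these texts requires the patient to be alive, on study, free of new antitumor therapy or assessed for DLT through day 21.

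Other sections deal with data collection. Protocol 8.5 collects AEs until 30 days after the last dose. Section 9 asks the investigator to pursue patients lost to follow-up and to obtain data from other centers. Appendix VIII has the SMC meet once the cohort's 21-day clinical data are in.

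**The concern.** DLT is the primary endpoint, and the no-more-than-1-in-6 rule drives both escalation and confirmation of the RD. A patient belongs in that denominator as a non-DLT only if the window was watched. Under a dose test alone, someone who takes 12 doses on 14/21 and then leaves without a DLT is evaluable, is not replaced and enters as DLT-free.

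The error runs one way. A DLT admits a patient at any dose, so incomplete observation can only add non-DLTs, which lowers the apparent DLT rate. Relapsed or refractory acute leukemia, where Protocol 1.2.5 expects severe disease-related events, is the setting in which early departures are most plausible. In AL, a patient who leaves may also lack the day 22 marrow on which Protocol 3.2.2.1 bases suspicion of the hematological DLT.

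**Working it through.** **The plan's own thresholds.** 0.85 × 14 = 11.9, so 12 doses. 0.85 × 21 = 17.85, so 18 doses. At 10 mg these are 120 mg and 180 mg, matching Protocol 11.2 and SAP 8. Both equal 85.7% of planned dose (12/14 and 18/21).

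**Window left after the threshold is met, with no missed doses.**

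- 14/21: 21 − 12 = 9 days, 9/21 = 42.9% (dosing days 13–14 and seven rest days).
- 21/21: 21 − 18 = 3 days, 3/21 = 14.3%.

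**Patients on 14/21, from the SAP 6.1 column headers.**

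- AL escalation: 3 + 3 + 4 + 4 + 8 + 7 + 7 = 36 (DL1, DL2, DL3A, DL4A, DL4B, DL5A, DL6).
- OHM escalation: 3 (DL5B). Escalation total: 39.
- Expansion: 19 + 16 + 16 = 51.

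**What happens to a patient who stops after dose 12 without a DLT.**

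- Death, loss to follow-up or full withdrawal of consent: days 13–21 cannot be, or may not be, observed.
- Start of other therapy: AE collection is still due to about day 12 + 30 = 42, but days 13–21 are confounded by the new drug.
- Stopping study drug only: AEs are still due. Whether the day 15 and 22 tests continue is not stated.

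In every case the patient is evaluable and not replaced.

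**Effect on escalation.** The documents give no DLT rate and no timing, so both are assumptions. Let p be the true 21-day DLT risk. With a constant hazard, a patient observed only to day 12 shows a DLT with probability p₁₂ = 1 − (1 − p)^(12/21). The rule escalates on 0/3, or on 1/3 followed by 0 of the next 3:

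P(escalate) = P(0/3) + P(1/3) × (1 − p)³.

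For p = 0.33 and full observation: 0.67³ = 0.301; 3 × 0.33 × 0.67² = 0.444; 0.301 + 0.444 × 0.301 = 0.434.

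With one of the first three truncated: 0.67^(12/21) = 0.7955, so p₁₂ = 0.205. P(0/3) = 0.7955 × 0.67² = 0.357. P(1/3) = 0.205 × 0.67² + 2 × 0.33 × 0.67 × 0.7955 = 0.444. The sum is 0.357 + 0.444 × 0.301 = 0.490.

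| Assumed p | None truncated | One of first three | Two | Three |
|---|---|---|---|---|
| 0.20 | 0.709 | 0.747 | 0.786 | 0.825 |
| 0.33 | 0.434 | 0.490 | 0.552 | 0.620 |
| 0.50 | 0.172 | 0.221 | 0.282 | 0.360 |

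For other timing at p = 0.33 with one truncated patient, the figure runs from 0.464 if 20% of DLTs fall after day 12 to 0.523 if 60% do.

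For RD confirmation (no more than 1 of 6), one truncated patient moves the probability from 0.655 to 0.688, 0.358 to 0.399 and 0.109 to 0.136 at the same three risks.

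**The case against.** The strongest reply is that the trial watches these patients anyway. AEs are collected for 30 days after the last dose whatever the reason for stopping, data from other centers must be sought, and the next dose level waits until the last treated patient has completed a cycle. The SMC sees 21-day data and may add patients (Protocol 3.3). An event counts as a DLT unless its relation to drug is definitely ruled out.

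This stands in part. It defeats an inference that everyone who stops after dose 12 goes unobserved: that fits only death, loss and full withdrawal of consent. It does not defeat the point, because these are duties to collect data or matters of discretion, and none changes who is evaluable or replaced.

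A reader might also infer that the day 15 and 22 tests lapse once drug stops, since Protocol 7.2.2 lists them under visits during study treatment and the end-of-therapy visit comes 35 ± 5 days after the last dose. The documents do not support that firmly. On 14/21 day 15 is a rest day for every patient, the synopsis sets weekly blood tests for the first three weeks with no on-drug condition, and Protocol 3.2.2.1 bases AL cohort decisions on the day 22 marrow. The matter is unclear, not shown.

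A reader might count all 39 + 51 = 90 patients on 14/21, of 141 enrolled, as bearing on the choice of dose. The 51 expansion patients were treated after the RD was set; they affect only the DLT rate reported at the RD.

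Finally, the study is complete (SAP 5). Replacement is no longer possible, and a definition introduced now is post hoc and removes only non-DLT patients. That is a reason to make it supportive, not to omit it.

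**Conclusion.** The gap is real and limited. Apart from patients with a DLT, evaluability depends only on dose. On 14/21 the threshold can be met with up to 9 of 21 days (43%) still to run, against 3 of 21 on continuous dosing. Observation is truly cut short only by death, loss or full withdrawal of consent; a change of therapy confounds days 13–21 instead.

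One such patient among the first three would raise the probability of escalating by about 0.04 to 0.06 across assumed risks of 20% to 50%. This rests on the assumed DLT risks, a constant hazard and departure right after dose 12. It concerns at most the 39 escalation patients on 14/21, and the number actually truncated, which may be zero, is not in the documents. The evidence does not show that the RD is wrong; it shows that the DLT table as planned cannot reveal whether truncation mattered.

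A related inconsistency affects who qualifies. Protocol 3.1.1 and 9 tie 12 and 18 days to schedule; Protocol 11.2 and SAP 8 tie them to disease. Read literally, the latter let an AL patient on continuous dosing qualify at 12/21 = 57.1% of dose, while an OHM patient on 14/21 can never reach 18 days.

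**What to change.** In SAP 8 and 12.3, keep the protocol-defined DLT population and add a second, supportive one: patients who had a DLT, or who took at least 85% of the planned cycle 1 dose and were assessed for DLT through day 21 (with the day 22 marrow where it applies) without new antitumor therapy.

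Show the DLT table by dose level under both definitions. List every patient evaluable under the protocol rule who died, withdrew, was lost or started other therapy before day 21, with the date of the last cycle 1 assessment. Reconcile the 12- and 18-day counts so that Protocol 3.1.1, 9 and 11.2 and SAP 8 rest on one stated basis.

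The cost is one definition, one extra table and one listing, with a slightly smaller evaluable number at some dose levels. The protocol's replacement wording can no longer be acted on in this study.
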